Importantly, anodal tDCS can modulate linguistic abilities in healthy individuals and improve language performance in patients with post-stroke aphasia, via modulation of effective connectivity in the brain (Fiori et al. 2018). Indeed, anodal tDCS affects structural plasticity in the auditory cortex of normal-hearing and noise-exposed rats (Paciello et al. 2018). These effects are thought to result from enhanced neuroplasticity that can occur as relevant groups of neurons are stimulated to fire together, thereby strengthening neural pathways and improving signal processing. Studies of tDCS and transcranial magnetic stimulation of auditory cortex are limited to normal hearing subjects and have demonstrated several perceptual effects including modulation of the mismatch negativity evoked response potential component, increased temporal resolution, phonetic categorization, and pitch discrimination (see review by (Heimrath et al. 2016)) as well as modulation of the right ear advantage in dichotic listening (Heimrath et al. 2020). However, tDCS has not been studied for enhanced rehabilitation of speech perception in patients with hearing loss.

4) Design & Procedures:

This prospective study involves the completion of a 4 week computer-based auditory training program while administering tDCS. Patients with a unilateral Cochlear Implant will be asked to complete 30-minute sessions of self-directed auditory training while administering tDCS, at least five times per week for 4 weeks. Subjects will be asked to complete daily electronic logs for adverse event reporting and documentation of auditory training compliance. Subjects will be provided with a customized learning and practice plan during the initial baseline visit and given instructions on use of the tDCS device. Subjects will be selected whose sentence recognition scores (AzBio) have plateaued below 65%, which provides an opportunity to detect a measurable improvement in response to the proposed intervention.

The following assessments/procedures will be performed at the MOSCH lab located in the [name]:

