Hearing and Speech Evaluation: Hearing thresholds and speech perception performance will be measured during the baseline visit, and 1 month and 6 month follow up visits using standard, validated and standard word and sentence lists presented in quiet and in noise (AzBio Quiet, AzBio +5/+10dB; CNC 50-item list) while the patient is wearing an appropriately programmed CI alone and/or with appropriately fitted contralateral hearing aid (if this is typically worn by the patient).

5) Study Schedule:

Visit 1/Baseline:

Subjects will undergo a screening visit to determine eligibility. The screening visit may be combined with a standard of care visit for patients already being seen for cochlear implant evaluation. Each participant will sign an informed consent before committing to any study-related tests or procedures and will include the following assessments:

- Obtain and document consent from potential participant on informed consent form (ICF).
- Conduct baseline hearing threshold and speech perception testing using standard audiological procedures (e.g., AzBio Quiet, AzBio +5/+10dB; CNC 50-item list) for screening for eligibility and baseline assessment
- Obtain patient reported outcome questionnaires (SSQ-12 and CIQOL)
- Auditory training and assignment of home-based personalized, computer-based rehabilitation/practice plan
- Orientation to tDCS equipment, determination of appropriate stimulation levels and electrode placement

- Conduct integrity evaluation of device using telemetry during initial tDCS trial.
- Repeat subset of speech perception assessment before, during and after the initial tDCS application.
- Instructions for completion of electronic daily diary to record adverse events and compliance of auditory training

The tDCS current will be programmed to 2.5mA prior to the start of integrity testing. If 2.5mA is intolerable, then the current will be reduced to 2.0mA. If a participant is still not able to tolerate 2.0mA, then this will be considered a screen fail and the subject will be removed from study.

Study participants meeting the screening criteria upon completion of the baseline visit will continue on study. Enrolled participants will be given a tDCS device to take home to complete study procedures with instructions to return it at the 1 month post-treatment visit to be completed in person.

Weeks 2-5 (Visits 2 – 5)

During the 30-day treatment period, subjects will be expected to complete the following:

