3. Sentence recognition scores (AzBio) are below 65% in quiet and/or word recognition scores (CNC) are below 75% in the implanted ear for \geq one year following cochlear implant activation.
4. Ability to access internet to conduct computer-based auditory trainings and weekly video visits with study team weeks 2–5

Exclusion Criteria

1. Non-English speaking
2. Diagnosis (documented or self-reported) of a psychiatric or neurologic condition, or any other comorbidities that may interfere with the study or increase the level of risk (such as dementia, seizures, legal blindness, brain tumor)
3. Implants, other than CI, above collar bone level that may interact with delivery of tDCS
4. Inability to or unwillingness to use electronic devices/computers, participate in video visits, or make required visits

7) **Subject Recruitment and Compensation:**

10 patients from the Duke Head and Neck and Communication Science clinics and/or the Duke Raleigh HNSCS Clinic will be recruited. Patients who meet the inclusion and exclusion criteria listed above will be approached for possible study participation after a member of the clinical care team asks the patient's permission to be contacted by the study team. The study coordinator (or member of the research team) will then review the records, and upon determination that the patient is deemed eligible for this protocol, the clinical research coordinator (CRC) will contact the patient. This may occur in clinic or via phone using an IRB approved phone script. If the patient indicates interest in study participation, the study coordinator will thoroughly explain the required elements of informed consent and all aspects of the study to the subject including inclusion/exclusion criteria, risks, benefits, and alternative to study participation. Up to 14 patients will be enrolled, allowing for 4 drop-outs.

Subjects will be compensated \$75 upon completion of the baseline visit (visit 1), \$100 upon completion of the one-month f/u visit (visit 6) and \$75 upon completion of the six-month follow up visit (visit 7) for total of \$250.

8) **Consent Process:**

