The primary outcome measures of efficacy will be speech perception performance in the best listening condition compared to baseline, progress within the computer-based rehabilitation program and patient report of improved daily communication function. Speech perception performance will be measured using validated and standard word and sentence lists presented in quiet and in noise (AzBio Quiet, AzBio +5/+10dB; CNC 50-item list).

For the primary outcome we are reporting straightforward proportions and will not be conducting any group comparisons. The prevalence with which adverse effects are reported will be determined for the study as a whole and for different time windows during the study. To address efficacy we would compare baseline speech perception and survey results with 1 and 6 month data.

Descriptive analysis will include mean and standard deviations, and may also include evaluate for improvement using paired t-test. Need for statistical consultation is likely to be minimal but will be sought if appropriate.

14) Data & Safety Monitoring:

The PI will ensure proper data and safety monitoring. Any serious adverse events will be reported by the PI to the IRB within 5 business days. Events that are considered both serious and unanticipated will be reported to the IRB within 24 hours of the PI's knowledge of the event. The PI will reconsider study design and procedures in discussion with the IRB should adjustments be warranted.

Adverse events will be monitored from the start of auditory training with tDCS at week 2 until the six-month follow-up visit at visit. The PI and study team will meet frequently to review patient reported adverse events.

The investigator's clinical judgment is used to determine whether a subject is to be removed from treatment due to an adverse event. In the event a subject requests to withdraw from protocol-required therapies or the study due to an adverse event.

Definition of unanticipated and serious adverse events requiring prompt reporting to the IRB are described below:

Unanticipated Problems

The Office for Human Research Protections (OHRP) considers unanticipated problems involving risks to subjects or others to include, in general, any incident, experience, or outcome that meets **all** of the following criteria:

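### The Visit 1 AzBio-quiet and CNC scores both decide entry and serve as baseline, which builds a small upward expected change into those scores; deciding eligibility on prior records would remove it

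*Combined protocol and SAP*

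**What the plan says.** All references are to the combined protocol and SAP.

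- **Section 5, Visit 1/Baseline.** Hearing and speech testing is done "for screening for eligibility and baseline assessment". The visit ends with a selection step: "Study participants meeting the screening criteria upon completion of the baseline visit will continue on study".
- **Section 6, inclusion criterion 3.** The ceiling is "Sentence recognition scores (AzBio) are below 65% in quiet and/or word recognition scores (CNC) are below 75% in the implanted ear", and it must have held for at least "one year following cochlear implant activation".
- **Section 4.** The ceiling is described differently: "Subjects will be selected whose sentence recognition scores (AzBio) have plateaued below 65" per cent, with no CNC alternative.
- **Section 7.** The coordinator reviews the records and judges the patient eligible before making contact.
- **Section 5 again.** There is further speech testing on the same day: "Repeat subset of speech perception assessment before, during and after the initial tDCS application". Nothing makes any of these repeats the baseline.
- **Section 13.** "To address efficacy we would compare baseline speech perception and survey results with 1 and 6 month data". The analysis is means and standard deviations, with an optional paired t-test. The efficacy outcome is speech perception in the best listening condition. There is one arm.

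**The concern.** A patient whose true score lies near the ceiling is admitted when Visit 1 happens to go badly and excluded when it happens to go well. The 1- and 6-month scores are not selected in this way. Among those who enter, the qualifying score is therefore too low on average and the follow-up score is not. This is regression to the mean. It needs no training effect, no tDCS effect and no true improvement.

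Purpose (b) of the study is the change in speech perception after the intervention. With no control arm to carry the same artefact, neither the mean change nor a paired t-test can separate it from a real gain. In expectation it always favours the intervention, and a pilot gain may inform whether a larger trial follows and how large it is.

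**Working it through.** The plan contains no figure for this bias, no score distribution and no power calculation, so there is nothing of its own to reproduce. From the documents come the cuts (65% and 75%), the 50-item CNC list and the 10 patients. Everything else below is assumed.

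**1. Direction, for one test with one cut.** Let the Visit 1 score be T + e1 and the follow-up score T + e2, with the same true score T. Let T have mean m and SD d, let the test SD be w, and let the cut be c. Entry requires T + e1 < c. Then

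expected change = (w²/s) × φ(a)/Φ(a), with s² = d² + w² and a = (c − m)/s.

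This is positive whenever w > 0 and the cut can exclude someone. For scale, the binomial error of a 50-item list is 100√(p(1−p)/50), which is 7.1 points at p = 0.50 and 6.1 at p = 0.75.

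Example with m = 60, d = 20, w = 7, c = 65:
- s = √(400 + 49) = 21.19
- a = 5/21.19 = 0.236
- φ/Φ = 0.388/0.593 = 0.654
- expected change = (49/21.19) × 0.654 = 1.5 points

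Over a wide grid (m 40 to 80, d 15 to 25, w 5 to 10) the formula runs from 0.2 to 7.7. The top value needs a source population averaging 15 points above the ceiling, a test SD of 10 and no prior record check.

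**2. The rules as written, by simulation with no true change.** Assumptions: AzBio true mean 45 to 65; SD 10 to 20; 50 or 100 effective AzBio items; CNC true mean equal to AzBio or 8 points lower; true correlation 0.85; independent binomial error at each test.

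| What decides entry | AzBio quiet | CNC |
|---|---|---|
| Section 6 and/or rule at Visit 1 | about 0 to 0.3 (median 0.04) | about 0 to 0.9 (median 0.25) |
| Same, and one prior record also qualifies | at most about 0.2 | at most about 0.6 |
| Section 4, AzBio alone at Visit 1 | about 0.2 to 3.0 | not an entry test |
| Same, and one prior AzBio also below 65% | about 0.15 to 2.1 | not an entry test |
| Prior records only | about 0 | about 0 |

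The and/or rule shrinks the bias because a patient with a good AzBio day can still enter on CNC. Wider assumptions (means up to 80, test SD up to 10) take the and/or figures to 0.5 for AzBio and 2.6 for CNC, or 0.3 and 1.1 if two prior records also had to qualify.

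**3. Effect on a t-test.** With n = 10 and w = 7, the SD of a change is 7√2 = 9.9 and its standard error is 9.9/√10 = 3.1 points. For an assumed two-sided 5% test, the chance of a falsely significant gain is 2.5% without bias. It becomes 3.5%, 6.3% or 13.6% with a bias of 0.5, 1.5 or 3 points.

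**4. The same-day repeat as baseline.** Split the test error into list error (SD 6) and day error (SD 3 or 5), with m = 60, d = 15 and the single 65% cut. A repeat on another list removes the list part only.
- Day SD 3: the total error variance is 36 + 9 = 45, so 9/45 = 20% of the bias remains, about 0.3 of 1.7 points.
- Day SD 5: the total is 36 + 25 = 61, so 25/61 = 41% remains, about 0.9 of 2.2 points.

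**The case against.** The strongest reply is that the protocol already selects on history. Criterion 3 asks for scores below the ceiling over at least a year, Section 4 speaks of a plateau, and Section 7 has eligibility judged from records before contact. One Visit 1 test cannot establish a year-long condition. If Visit 1 in practice overturned nobody, the bias would be about zero. This stands as a limit on size: prior scores reduce the bias in every scenario. It does not remove the point, because Section 5 still makes continuation depend on the criteria being met after Visit 1, and no section says how often that would overturn the record review.

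A second reply is that this is a feasibility study of 10 patients with a descriptive analysis, and that a bias of a few tenths of a point is lost in a standard error of about 3 points. That is fair for the and/or rule. It is less so for the AzBio-only reading.

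A reader might infer that the whole efficacy comparison is inflated, or that a bias near 3 points is to be expected. The documents support neither. Entry uses AzBio in quiet and CNC in the implanted ear. AzBio in noise, the questionnaires and a separately tested best listening condition are affected only through error shared on the day. The 3.0-point figure needs Section 4's AzBio-only wording and a population centred at the ceiling.

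**Conclusion.** The concern holds as a modest bias, certain in direction and uncertain in size. It applies to the AzBio-quiet and CNC scores in the implanted ear, in expectation, for as long as the Visit 1 score can exclude a participant. Under the stated assumptions it is mostly below 1 point with the literal and/or rule. It could reach 2 to 3 points only if AzBio alone decides entry and recruits lie close to the ceiling. Sections 4 and 6 differ on exactly this, so the protocol itself leaves the size open. Day-to-day variation beyond binomial error would enlarge all of these figures.

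It would be wrong to conclude that any observed gain is an artefact of selection, or that the feasibility and adverse-event proportions are compromised. The latter do not use the baseline score at all.

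**What to change.** 1. In Sections 5 and 6, state that criterion 3 is decided on the prior clinical scores already reviewed under Section 7. The one-year and plateau wording needs those records in any case.
2. State that no participant is excluded on the Visit 1 speech score, and in Section 13 name Visit 1 as the unselected baseline. The simulated bias is then about 0.
3. Reconcile the ceilings in Section 4 (AzBio only) and Section 6 (AzBio and/or CNC).

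The cost is a change of wording, with no added visit or test. The downside is that an occasional participant will score at or above the ceiling at Visit 1 and have less room to improve.

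If the Visit 1 score check must stay, the repeat taken before tDCS, on a different list, could serve as baseline. This is only a partial fallback. It shares the day's error with the qualifying test, and it covers only a subset of the tests, so it might have to be extended to include the outcome measures.

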It's possible that tDCS pads may cause damage to hearing aid microphones if they get wet. Therefore, participants who wear a contralateral hearing aid will be instructed to remove it prior to and during the use of tDCS.

Participants will record daily symptoms via a link to a REDCap survey. REDCap will be programmed to alert the PI and/or SC of symptoms with an intensity level reported at 8 or above on the AE/symptom survey, regardless of the duration indicated (refer to table below). The PI, SC, or delegate will contact the patient to obtain additional information and determine if tDCS should be discontinued, and if a referral for medical evaluation is needed.

In conclusion, given the low risk of tDCS and its combination with CI, the risk/benefit is favorable since improvement in the patients’ speech perception due to the administration of tDCS could improve their quality of life.

12) Costs to the Subject:

The study does not involve any costs to subjects. Costs for the audiological assessments will be covered by the study. tDCS devices for in-home use will be provided to study participants at no charge and returned at the end of the 1-month follow-up visit.

13) Data Analysis & Statistical Considerations:

The primary outcome measures of feasibility are: 1) proportion of eligible CI patients who expressed interest in the study; 2) proportion of selected participants who completed tDCS training and demonstrated competence in the office and subsequently at home during remote visits; 3) proportion of participants who completed most or all of the proposed intervention protocol; 4) proportion who completed relevant appointments, and reasons for any missing data; 5) acceptability of patient incentive; 6) patient report of ease/difficulty carrying out the protocol via a patient survey at Visit 2; 7) proportion of people with any adverse events, and 8) other feasibility and acceptability metrics consistent with the latest guidelines on pilot studies (Eldridge et al. 2016). After each in-office tDCS application and at the immediate one month post-intervention Visit 6, the site of tDCS stimulation and the CI site will be visually examined for any skin irritation or tenderness and the internal and external CI devices will be examined for signs of abnormal function. Adverse effects of tDCS will be measured by the intensity and duration of symptoms recorded on the daily diary.

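### Does the first feasibility outcome, interest among eligible patients, need a stated denominator and a count of patients who refuse contact?

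*Combined protocol and SAP*

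**What the plan says.** Section 13 lists eight feasibility measures, the first being the "proportion of eligible CI patients who expressed interest in the study". It gives no time point or data source for either count, and says that the primary outcome will be reported as simple proportions with no group comparison.

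Eligibility appears at three places:

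- Section 7 opens with "Patients who meet the inclusion and exclusion criteria listed above will be approached for possible study participation". The same sentence places that approach after the care team has asked for "permission to be contacted by the study team".
- Section 7 continues that the coordinator "will then review the records, and upon determination that the patient is deemed eligible for this protocol", contact is made. Then: "If the patient indicates interest in study participation, the study coordinator will thoroughly explain the required elements of informed consent".
- Section 5, under Visit 1/Baseline, says "Subjects will undergo a screening visit to determine eligibility", and that "Each participant will sign an informed consent before committing to any study-related tests or procedures".

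The document describes no log of patients who refuse contact. The eighth measure in Section 13 promises further metrics in line with a cited pilot-trial guideline but names none.

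**The concern.** A proportion whose denominator is not fixed can be computed in more than one way, and this one is the first listed measure in a trial whose title and first purpose concern safety and feasibility. If eligibility is judged after permission to contact, patients who turn down the care team never enter the denominator. They may be less interested than those who agree, so the reported figure could overstate interest among all eligible patients. A reader planning a larger study might take it for the wider quantity. Refusals that nobody tallied cannot be reconstructed at analysis.

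A related loss comes through the fourth exclusion criterion in Section 6, "Inability to or unwillingness to use electronic devices/computers, participate in video visits, or make required visits". A patient who is put off by the demands of the study may be classed as ineligible and not as uninterested.

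**Working it through.** The plan states no target, expected rate, denominator or precision for this outcome, so there is no figure to reproduce. The check has two parts: what the text implies, and how far the possible denominators could differ.

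**Which denominator the text implies**

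- *All eligible patients asked for permission.* This rests on the opening of Section 7. The full sentence, however, puts the approach after the permission request, and the next sentence puts the recorded eligibility decision later still. A patient who refuses contact has no eligibility decision by the study team.
- *Patients who agreed to contact and were found eligible on record review.* Section 7 runs: permission, review, eligibility decision, contact, interest. The last three of these supply the denominator and numerator of the outcome in order, and both counts arise from steps the study team itself carries out.
- *Patients confirmed eligible at Visit 1.* All of them have already consented, so the proportion is 100% by construction. The outcome wording also counts against this reading: the first measure speaks of patients, while the second and third speak of participants. The first is a measure taken before enrolment.

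The second reading is the natural one and can be computed from the steps described.

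**How far the first two could differ**

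Let p be the share who give permission, e the eligibility of refusers relative to those who agree, and k the interest of refusers relative to those contacted. Then

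factor = (interest among eligible patients contacted) / (interest among all eligible patients asked) = [p + (1 − p)e] / [p + (1 − p)ek].

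None of p, e or k is in the documents; all values below are assumptions.

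| Assumption | p = 0.90 | p = 0.75 | p = 0.50 |
|---|---|---|---|
| e = 1, k = 0 | 1/0.90 = 1.11 | 1/0.75 = 1.33 | 1/0.50 = 2.00 |
| e = 1, k = 0.5 | 1/0.95 = 1.05 | 1/0.875 = 1.14 | 1/0.75 = 1.33 |
| e = 0.5, k = 0 | 0.95/0.90 = 1.06 | 0.875/0.75 = 1.17 | 0.75/0.50 = 1.50 |
| k = 1, any e | 1.00 | 1.00 | 1.00 |

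The value 1/p is a maximum only when e ≤ 1 and k ≥ 0. With e = 1.5, k = 0 and p = 0.75 the factor is (0.75 + 0.375)/0.75 = 1.50, above 1/0.75 = 1.33. The direction is also assumed: with e = 1, k = 1.5 and p = 0.75 the factor is 1/(0.75 + 0.375) = 0.89, an understatement.

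**Whether a tally of refusals would recover the wider quantity**

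Take, for illustration, 14 interested among 20 contacted, or 70%, with 10 refusers, none of them interested. If all 10 are eligible, interest among eligible patients asked is 14/30 = 47%. If only 5 are eligible, it is 14/25 = 56%. The tally supplies the 10 but not the number eligible, because records are reviewed only after permission. A proportion among all patients asked is therefore not a proportion of eligible patients.

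**The case for a change.** The strongest case for a change is that the remedy is cheap and the loss permanent. Clinic staff already ask the permission question, so a de-identified yes/no count would cost little, and without it the number of refusals is gone. The plan takes care over losses elsewhere: its fourth feasibility measure asks for reasons for missing data, and Section 15 records the reason and date of each withdrawal. Nothing similar is described for losses before enrolment, which is where the first measure sits.

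Part of this stands. The document does not name the denominator, it describes no count of refusals, and such a count would be useful context in a report. It does not make the plan wrong. The text is silent on refusals and does not exclude them; a recruitment log may exist in the IRB submission or the phone script, neither of which is available here. Someone who declines contact has not declined the study as explained, so counting that person as uninterested would be a choice with its own bias. The same holds for the fourth exclusion criterion: patients excluded under it are ineligible as the protocol defines the term, so leaving them out of a proportion of eligible patients follows the definition.

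**Conclusion.** No change to the plan is needed. The missing denominator is a gap that the protocol's own recruitment sequence fills: followed as written, Section 7 yields interest among patients who agreed to contact and were found eligible on review. That is a valid descriptive proportion, provided the report says that it is conditional on permission to contact, which an analyst would do as a matter of course.

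The size and direction of any difference from interest among all eligible patients cannot be determined from the documents. The range of 1.00 to 2.00 rests wholly on assumed permission rates of 50% to 90% and on refusers being no more often eligible and no more interested than those contacted; outside those conditions it can be larger, or below 1. A tally of refusals would describe the recruitment funnel but would not identify the wider proportion. No decision threshold, sample size, test, or safety, adherence or speech result depends on this figure, in an uncontrolled pilot that aims for 10 patients and enrols at most 14.

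This conclusion assumes that the coordinator's record review and contacts are documented well enough to count, which computing the outcome on this reading already requires.
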